9.1.1. Criteria for Assessment of Relative Bioavailability

90% confidence intervals for AUC_{last} and AUC_{inf} will be calculated, with intervals between 80% and 125% indicating equivalent relative bioavailability.

9.2. Pharmacodynamic Analyses

Total urine output, total urinary sodium excretion, and total urinary potassium excretion from times 0-6, 0-8 and 0-12 hours will be tabulated by summing the concentration*volume of each collection interval across the time span specified and summarized using descriptive statistics including N, mean, standard deviation (SD), coefficient of variation (CV%), median, minimum, maximum, geometric mean and geometric CV% analyzed by treatment in the BA population.

A repeated measures, mixed model analysis will be used to evaluate the mean difference between SC and IV across all time points. This analysis will account for within-subject correlations and between-subject variability. The model will include fixed effects for treatment (SC vs IV), time, and treatment-by-time interaction, and a random effect for subjects.

- 95% Confidence Intervals (CI) for the difference between SC and IV administration will be calculated for all measured parameters.
- P-values will be determined for the comparison of subcutaneous and intravenous administration methods, using the mixed model analysis.
- The means and 95% CIs of the parameters will be plotted at the specified time points: 0-6,0-8 and 0-12 hr.

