6.2. Pharmacodynamic Endpoints

Urine will be collected from spontaneous voids in 1-hour increments for the first 8 hours and in 2-hour increments up to 12 hours post-dose. Total urine output, urinary sodium, and potassium excretion for each collection interval ((0-1), (1-2), (2-3), (3-4), (4-5), (5-6), (6-7), (7-8), (8-10) and (10-12) hours after initiation of dosing) will be recorded.

The following PD parameters will be evaluated for IV furosemide and SC SCP-111 subcutaneous administration:

Urine Output:

- Measured at 0-6 hours, 0-8 hours, and 0-12 hours
- The sum of urine output for intervals 0-1, 1-2, 2-3, 3-4, 4-5 and 5-6 comprise 0–6-hour urine output.
- The sum of urine output for intervals 0-1, 1-2, 2-3, 3-4, 4-5, 5-6, 6-7 and 7-8 comprise 0–8-hour urine output.
- The sum of urine output for intervals 0-1, 1-2, 2-3, 3-4, 4-5, 5-6, 6-7, 7-8, 8-10 and 10-12 comprise 0–12-hour urine output.

Urinary Sodium Excretion:

- Measured at 0-6 hours, 0-8 hours, and 0-12 hours
- Calculated as: Urinary Sodium Excretion=Total Urine Output (L) × Sodium Concentration (mEq/L)

Urinary Potassium Excretion:

- Measured at 0-6 hours, 0-8 hours, and 0-12 hours
- Calculated as: Urinary Potassium Excretion=Total Urine Output (L) × Potassium Concentration (mEq/L)

Example Calculation:

- **Interval: 0-1 hour**

Total Urine Output=0.5 L

Sodium Concentration=100 mEq/L

Urinary Sodium Excretion=0.5 L×100 mEq/L=50 mEq

- **Interval: 1-2 hours**

Total Urine Output=0.4 L

Sodium Concentration=90 mEq/L

Urinary Sodium Excretion=0.4 L×90 mEq/L=36 mEq

Continue this calculation for each subsequent interval (e.g., 0-1, 1-2, 2-3, 3-4, 4-5, 5-6, 6-7, 7-8, 8-10, and 10-12 hours) to obtain the total urinary sodium excretion for each time period.

Same calculations are conducted to calculate urinary potassium excretion for each interval.

The sum of intervals 0-1, 1-2, 2-3, 3-4, 4-5 and 5-6 comprise 0-6 hour urinary sodium/potassium excretion.

The sum of intervals 0-1, 1-2, 2-3, 3-4, 4-5, 5-6, 6-7 and 7-8 comprise 0-8 hour urinary sodium/potassium excretion.

The sum of intervals 0-1, 1-2, 2-3, 3-4, 4-5, 5-6, 6-7, 7-8, 8-10 and 10-12 comprise 0-12 hour urinary sodium/potassium excretion.

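### The SAP's PD mixed model treats overlapping 0-6, 0-8 and 0-12 h totals as separate information and omits period, so its SC-IV intervals and p-values are not calibrated

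*SAP*

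**What the plan says.** SAP 9.2 plans a repeated-measures mixed model that "will be used to evaluate the mean difference between SC and IV across all time points". It states that "This analysis will account for within-subject correlations and between-subject variability", and then lists the terms: "The model will include fixed effects for treatment (SC vs IV), time, and treatment-by-time interaction, and a random effect for subjects". From this model it promises p-values, and "95% Confidence Intervals (CI) for the difference between SC and IV administration will be calculated for all measured parameters". Means and intervals "will be plotted at the specified time points: 0-6,0-8 and 0-12 hr".

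SAP 6.2 defines those time points as sums that share intervals. At the short end, "The sum of intervals 0-1, 1-2, 2-3, 3-4, 4-5 and 5-6 comprise 0-6 hour urinary sodium/potassium excretion". At the long end, "The sum of intervals 0-1, 1-2, 2-3, 3-4, 4-5, 5-6, 6-7, 7-8, 8-10 and 10-12 comprise 0-12 hour urinary sodium/potassium excretion". Urine output is built the same way.

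For the same two-period design, SAP 9.1 analyses the PK parameters with sequence, subject within sequence, treatment and period. Protocol 3.2.2 calls for SC and IV to be compared at 6, 8 and 12 hours. Protocol 8.5 describes the PD comparison as descriptive. SAP 9 gives the SAP precedence over the protocol.

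**The concern.** A random subject effect alone makes the three totals from one period independent and equally variable, given the subject. Nesting breaks both assumptions, because the 0-6 h urine is counted again inside 0-8 h and 0-12 h. A high-output period raises all three totals together. The treatment contrast should be judged against how the SC-IV difference varies between subjects. The listed model judges it against a pooled residual in which that variation has a small weight.

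If the phrase about all time points means a contrast averaged over the windows, that average is also not an endpoint named in the protocol.

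Leaving out period is a separate gap. It does not narrow the interval. It adds a real period difference to the residual and biases the estimate slightly when the two sequences differ in size.

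At stake is whether the reported PD intervals and p-values have the error rates they claim.

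**Working it through.** **Inputs from the documents.** Two sequences, 1:1; 21 enrolled for 18 completers; 95% intervals, taken as two-sided 5%; three nested totals per period. The only design figure stated is n = 18 for AUCinf. Reading intra-subject CV as half of 30.6-31.6%, with a true ratio of 0.95 or 1.05, power at 18 is 93.2-95.0%, so the claim of at least 90% holds. No PD variance, correlation, period effect or urine profile is given, so everything below is a range over assumptions. That the three windows are the model's time levels is inferred from the plotting bullet.

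**What an average over windows estimates.** With U for output in a block, the mean of the three totals is U(0-6) + (2/3)U(6-8) + (1/3)U(8-12).

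**Degrees of freedom at n = 18.** Listed model: 17 × 5 = 85. Crossover model: 18 − 2 = 16. At n = 21 these are 100 and 19.

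**Error term.** The 85 df comprise 17 for treatment × subject, 34 for window × subject and 34 for treatment × window × subject. Hence

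E(MSE) = [MS(trt × subj) + 2 MS(win × subj) + 2 MS(trt × win × subj)] / 5.

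The right error for the averaged contrast, absent a period effect, is MS(trt × subj) alone. The ratio of the listed CI width to the crossover CI width is therefore at least √(1/5) × 1.988/2.120 = 0.42. Window × subject variance can push it above 1. REML random-intercept fits gave the same standard error as this ANOVA form.

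**Equal variances, within-period correlation r.** Here MS(trt × subj) is proportional to 1 + 2r and the other two to 1 − r. The width ratio is √[(1 − 0.4r)/(1 + 2r)] × 1.988/2.120; at r = 0.5 this is √(0.8/2) × 0.938 = 0.59. Simulated false-positive rates for the averaged contrast (9+9 subjects, 8,000 runs per cell; period effect in within-subject SDs):

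| r | CI width ratio, no period effect | No period effect | 1 SD | 2 SD |
|---|---|---|---|---|
| 0 | 0.94 | 4.8% | 2.6% | 0.4% |
| 0.25 | 0.73 | 12.8% | 7.6% | 1.9% |
| 0.5 | 0.59 | 21.7% | 14.6% | 4.7% |
| 0.7 | 0.51 | 27.7% | 19.9% | 8.1% |
| 0.9 | 0.45 | 35.5% | 26.1% | 11.1% |
| 0.99 | 0.42 | 37.6% | 28.1% | 12.6% |

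**Nested totals, original scale.** 108 combinations, 3,000 runs each: cumulative share by 6 and 8 h of 97/99% (front-loaded), 82/91% (declining) or 50/67% (flat); subject CV 20-60%; subject-by-period CV 5-30%; interval CV 20-50%.

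| Quantity | Front-loaded or declining | Flat |
|---|---|---|
| CI width ratio, averaged contrast | 0.42-0.50 | 0.47-1.19 |
| False positives, averaged contrast | 30-42% | 2-33% |
| 0-6 h | 7-15% | 0-3% |
| 0-8 h | 8-16% | 0-8% |
| 0-12 h | 9-18% | 1-23% |

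On the ln scale the averaged contrast gave 29-41% and single windows 7-17%. The per-window crossover model gave 3.5-6.1% over both scales.

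**A separately coded simulation** (20,000 trials per scenario; 9+9, 10+8 and 11+10) gave 30-37% for the averaged contrast with no period effect, in scenarios without large between-subject spread in the later blocks. With such spread the rate was 8.5%. With a large period effect and no other shared within-period error it was 1.4% at 9+9. The crossover analysis gave 4.7-5.3% throughout.

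**Bias from omitting period.** It equals (n1 − n2)/n times the period effect. For a 1-SD effect this is 2/18 = 0.11 SD at 10+8, 1/21 = 0.05 SD at 11+10, and zero at 9+9.

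**The case against.** The strongest reply is that SAP 9.2 makes two commitments, to within-subject correlation and to between-subject variability. The subject effect serves the second, and a residual covariance could serve the first. An unstructured residual would remove most of the correlation problem. That reading is possible, but the SAP names no such structure, its list of terms stops at the subject effect, and period would still be missing.

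Second, the largest rates belong to the averaged contrast, which is only one reading. The treatment-by-time term and Protocol 3.2.2 point at least as naturally to per-window contrasts, where the range is 0-23% with mixed direction. This stands, and the averaged-contrast figures should be read as conditional. SAP 6.2 also records ten separate intervals. With those as the time levels (323 residual df), the averaged contrast ran from 0% to 51%, so that reading is not calibrated either.

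Third, the mix of simulated profiles was chosen, not observed. How often the rate is too high across the grid is therefore not a probability for this trial. That stands too.

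Fourth, a mixed model could use a subject with a window missing in one period, and separate crossover analyses could not. SAP 4.4 already excludes a subject with a missing subinterval from the affected window, so little is lost.

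Finally, the scale is not stated outright, but SAP 9.2 speaks of differences and means, so the original scale is the ordinary reading. This is a minor clarification.

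**Conclusion.** The concern holds, conditional on the listed terms being followed as written. The SC-IV intervals and p-values for urine output, sodium and potassium would then have error rates set by unknown variances: most often above 5%, in some settings well below it. In the nested-total grid the averaged contrast ran at 12% or more in 104 of 108 combinations, and its interval was too wide in one. These counts describe the assumptions made, not the likelihood in this trial. The conclusion that does not depend on them is the contrast in behaviour: the crossover model stayed near 5% everywhere it was tried.

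The consequence is limited. The PD objective is to describe, no success criterion uses these tests, and the primary AUC comparison and the descriptive PD tables are unaffected. The point should be fixed, but it does not threaten the trial's main result. Confidence is medium, because the size depends on PD variances and on how the model would actually be coded.

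**What to change.** For each of the three PD parameters and each of the three windows, replace the listed model with the SAP 9.1 crossover model (sequence, subject within sequence, period, treatment), in the BA population that SAP 9.2 already uses for its PD summaries. State the scale in advance. Report the SC-IV difference, or the ratio if ln-transformed, with its 95% interval and p-value. Drop any average over overlapping windows.

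Keeping a repeated-measures model is a possible alternative if period is added and an unstructured covariance across the three totals within period is named; this was not simulated.

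The change needs SAP wording and model code only, and no new data. It leaves 16 error degrees of freedom instead of 85 and, in most scenarios tried, gives wider intervals, chiefly for 0-12 h. With evenly spread output the 0-6 h interval becomes narrower.

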5.3. Method of Assigning Subjects to Treatment Groups

Subjects will be randomly assigned in a 1:1 ratio to 1 of 2 treatment sequences to receive both IV furosemide and SC SCP-111 in the abdomen in Crossover Periods (ie, IV followed by SC or vice versa).

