2. SAMPLE SIZE

In one study, the average coefficient of variation for furosemide AUC_{inf} following a 20 mg dose by the intravenous, oral, and sublingual routes of administration were 50%, 25%, and 33%, respectively ([Haegeli, et al. 2007](#)). In another study, the coefficient of variation for AUC_{inf} following 2-40 mg intravenous doses 2-hours apart was 31.6% and 30.6% for an 80 mg, 5-hour subcutaneous infusion ([Sica DA, et al. 2018](#)).

Assuming an intra-subject variability is approximately $\frac{1}{2}$ of total variability for the primary pharmacokinetic parameter AUC_{inf} and the test reference would fall within 95% to 105% at a significance level of 0.05, a minimum sample size of 18 subjects would be required to establish bioequivalence between test and reference products (defined as 90% CI for AUC_{inf} Geometric mean ratio SC injection to IV injection of furosemide within 80-125% interval) with a priori statistical power of at least 90%.

21 subjects will be enrolled to ensure 18 subjects complete the study through the Follow-up Phase.

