4.4. HANDLING OF MISSING DATA

No plasma concentration estimates will be imputed for missing values. Missing values will be treated as if they were not scheduled for collection and only those

samples with reported concentration values will be included in the pharmacokinetic and statistical analysis.

Missing values for urine collections will not be imputed. Any subject with a missing value for any subinterval (e.g. 0-1 hour) involved in the 0-6, 0-8 or 0-12 results will be excluded from statistical analyses for the interval affected.

No imputation of missing data will be done for any other data. To handle missing or partial AE and concomitant medication dates, the following rules in 5.4.1 will be applied.

4.4.1. For Partial Start Dates:

1. If the year is unknown, then do not impute the date but assign a missing value.
2. If the month is unknown, then:
 - i. If the year matches the year of the first dose date, then impute the month of the dose date.
 - ii. Otherwise, assign "January."
3. If the day is unknown, then:
 - i. If the month and year match the month and year of the first dose date, then impute the day of the dose date.
 - ii. Otherwise, assign "01."

4.4.2. For Partial End Dates:

1. If the year is unknown, then do not impute the date but assign a missing value.
2. If the month is unknown, then assign "December."
3. If the day is unknown, then assign the last day of the month.

After implementing the rules above, to determine whether AEs (or medications) with missing start or stop dates are pre-treatment or on/after first or second treatment, the following strategy will be used:

1. If both start date and stop date are missing, then the most conservative approach is taken, and the AE (or medication) is classified as treatment emergent (or concomitant medication).
2. If the start date is missing but the stop date is not missing and is on or after the day of study dose administration for Period 1 or 2, then the most conservative approach is taken, and the AE (or medication) is treatment emergent (or concomitant medication).
3. If the start date is missing but the stop date is not missing and is before the day of study dose for Period 1 and after the date of signed informed consent, then the AE (or medication) is not a TEAE (or prior medication).

4. If the start date is not missing but the stop date is missing, then the most conservative approach is taken, and medication is concomitant while the AE is defined by start date.

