8. ANALYSIS POPULATIONS

The statistical analyses and summaries will be based on the study populations detailed below.

The subject demographics, baseline characteristics and the other endpoints will be based on the Full Analysis Set (FAS) population. The PK Analysis will be performed on the Bioavailability (BA) population.

- **Full Analysis Set (FAS) Population:** This includes all participants who were randomized in the study, regardless of whether they completed the study as per protocol.
- **Pharmacokinetic (PK) Population** will include all randomized subjects who receive full 80 mg dose of furosemide study drug AND have sufficient samples collected for estimation of pharmacokinetic parameters.
- **Bioavailability (BA) Population** will include all subjects in the PK population who have a sufficient number of samples collected for estimation of pharmacokinetic parameters after receiving BOTH IV furosemide and SC SCP-111.

All Safety analyses will be based on the safety population.

- **Safety Population** will include all randomized subjects who received at least 1 dose of either study drug and have provided at least 1 post-baseline safety assessment.

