9.1. Pharmacokinetic Analyses

The analyses will be performed on subjects in the Bioavailability Population.

Derived plasma PK parameters will be tabulated and summarized by treatment. Descriptive statistics for PK parameters (C_{max} , T_{max} , AUC_{last} , AUC_{inf} , AUC_{ext} , λ_z , $t_{1/2}$, V , V_z/F , CL , CL/F , and F) will include the arithmetic mean, CV%, SD of the arithmetic mean, median, minimum, maximum, and N. The geometric mean and geometric CV% will be estimated for C_{max} , AUC_{last} , and AUC_{inf} , only.

Statistical analyses will be performed using the General Linear Models (GLM) procedure of the SAS statistical program (PC version 9.4). The naturally log-transformed (ln-transformed) pharmacokinetic parameter estimates (for C_{max} , AUC_{last} , and AUC_{inf} , only), as well as the concentrations at each scheduled sample time will be evaluated by analysis of variance.

The statistical model will contain the main effects of sequence, subject nested within sequence, treatment and period. F-ratios for testing main effects will be constructed using the mean square term for the effect as the numerator and the mean square error term from the ANOVA as the denominator. The F-ratio to test for sequence effects will be constructed using the type III mean square term for sequence as the numerator and type III mean square for subjects nested within sequence as the denominator. Hypothesis testing will be conducted at $\alpha = 0.05$, except in the case of sequence effects which uses $\alpha = 0.10$.

The PK Analysis report will discuss any statistically significant effect found for AUC or C_{max} .

The intra-subject coefficient of variation will be estimated from the mean square error term (MSE) of the ln-transformed (loge) results as:

$$100\% * \text{SQRT}(e^{\text{MSE}} - 1)$$

Confidence Intervals (90%) for the area under the curve (AUC) and peak concentration (C_{max}) comparisons are to be calculated by the t-test approach (2,1 sided) at $\alpha = 0.10$ overall, $\alpha = 0.05$ each side:

$$\text{Interval Lower Limit} = (X_{SC} - X_{IV}) - Se * t_{\alpha/2}$$

$$\text{Interval Upper Limit} = (X_{SC} - X_{IV}) + Se * t_{\alpha/2}$$

Where X_{SC} , X_{IV} are the SC SCP-111 and IV furosemide treatment least-squares means, respectively.

SE is the standard error of the estimated difference between means from the SAS estimate statement.

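### The PD model in SAP 9.2 omits period: if a period effect exists, unequal sequences bias the SC−IV difference slightly and the 95% CI is wider than needed

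*SAP*

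**What the plan says.** SAP 9.2 gives the PD model as a repeated-measures mixed model with "fixed effects for treatment (SC vs IV), time, and treatment-by-time interaction, and a random effect for subjects", and adds: "This analysis will account for within-subject correlations and between-subject variability". It yields 95% CIs and p-values for SC against IV. Time here means the collection windows 0-6, 0-8 and 0-12 h, which the same section names. The SAP's abbreviation list defines period separately, as a phase of the crossover.

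For PK in the same subjects, SAP 9.1 says: "The statistical model will contain the main effects of sequence, subject nested within sequence, treatment and period". Its adjustment for dosing groups is limited to the PK parameters. Protocol 3.2.2 asks only for suitable tests, Protocol 8.5 plans a descriptive PD comparison, and SAP 9 gives the SAP precedence. Nothing adds period to the PD model.

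Three further passages bear on balance and correlation:
- Size and allocation: "21 subjects will be enrolled to ensure 18 subjects complete the study through the Follow-up Phase" (SAP, Sample Size) and "Subjects will be randomly assigned in a 1:1 ratio to 1 of 2 treatment sequences" (Protocol 5.3).
- Missing urine (SAP 4.4): "Any subject with a missing value for any subinterval (e.g. 0-1 hour) involved in the 0-6, 0-8 or 0-12 results will be excluded", with the exclusion applied to the affected window.
- Nested windows (SAP 6.2): "The sum of intervals 0-1, 1-2, 2-3, 3-4, 4-5 and 5-6 comprise 0-6 hour urinary sodium/potassium excretion". The 0-8 and 0-12 h totals contain the same intervals.

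**The concern.** In a two-period crossover, any change between Period 1 and Period 2 enters every SC−IV difference, with opposite sign in the two sequences. If the sequences are equal in size, the change cancels from the mean but stays in the residual. If they are unequal, part of it remains in the estimate. Fitting period removes both effects.

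Equal sequences cannot be relied on. An odd 21 cannot split evenly, and exclusion by window lets the split differ between 0-6, 0-8 and 0-12 h. Neither a small bias nor lost precision would be visible in the CIs and p-values that SAP 9.2 reports.

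**Working it through.** **The plan's own figure.** The documents give no PD variance, period effect or power. The only computed design figure is 18 completers, for AUCinf. Halving the stated 31.6% CV gives 15.8%. With a ratio of 0.95, two one-sided tests need 16 subjects for 90% power and have 93.2% at 18. Halving 33% gives 16.5% and exactly 18 (91.3%). So the figure is reproducible if half is applied to the CV, but it says nothing about PD.

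**Bias.** Let n1 be IV-then-SC subjects, n2 SC-then-IV subjects, n = n1+n2, τ the true SC−IV difference and π the Period 2 minus Period 1 effect. The paired difference has mean τ+π in the first sequence and τ−π in the second. Without period, the estimate for complete pairs is τ + π(n1−n2)/n. For an assumed π of 10% of the mean:
- 9/9: 0
- 11/10: 10 × 1/21 = 0.5%
- 10/8: 10 × 2/18 = 1.1%
- 11/7: 10 × 4/18 = 2.2%

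The bias scales with π, so 20% doubles these figures.

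**Likely splits.** Assume 11/10 are randomised and 3 of the 21 drop out at random; C(21,3) = 1330.
- 9/9: 55 × 10 / 1330 = 41%
- 10/8 or 8/10: (11 × 45 + 165) / 1330 = 50%
- 11/7: 120 / 1330 = 9%

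**Precision at 9/9, one window.** Let σd be the SD of the paired difference. Without period the expected variance is σd² + π²·n/(n−1) on n−1 = 17 df (t = 2.1098). With period it is σd² on n−2 = 16 df (t = 2.1199). At an assumed within-subject CV of 20%, σd = 20√2 = 28.3 and σd² = 800.
- With period: 2.1199 × 28.3/√18 = 14.1
- Without, π = 10: 2.1098 × √(800 + 105.9)/√18 = 15.0
- Without, π = 20: 2.1098 × √(800 + 423.5)/√18 = 17.4

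These use the root of the expected variance. The average half-widths in simulation (200,000 trials per setting) are slightly smaller: 13.9, 14.7 and 17.2. Power for an assumed true 20% difference is 80% with period, and 77% or 65% without it for π = 10% or 20%.

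**Break-even.** Omitting period keeps one df. The widths are equal at π/σd = √{[(2.1199/2.1098)² − 1] × 17/18} = 0.095, which is 0.095 × 28.3 = 2.7% of the mean at CV 20%. With no period effect, the interval without period is 0.995 times as wide as the one with it.

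**False positives from omitting period.** With within-period correlation handled, CV 10-30% and π 0-30%, the rate at 9/9, 11/10, 10/8 and 11/7 is 0.0-5.0% without period and 4.9-5.1% with it. At these splits the inflated variance outweighs the bias.

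**Separate check: covariance.** Suppose the model were read as random subject plus independent residuals. Let ρ be the within-period correlation between windows and σ² the within-subject variance. At 18 complete pairs this reading has 85 residual df. Of these, 17 have mean square σ²(1+2ρ) and 68 have σ²(1−ρ), so the average is σ²(1−0.4ρ). The SC−IV difference averaged over windows really varies in proportion to σ²(1+2ρ). Its standard error is therefore understated by the factor √[(1+2ρ)/(1−0.4ρ)]: 1.58, 1.96 and 2.16 at ρ = 0.5, 0.8 and 0.95. The two-sided 5% test then rejects about 21%, 31% and 36% of the time with no true difference. Simulation gives 21-22%, 32% and 37%. The period effect plays no part in this.

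**The case against.** The strongest case against is that every consequence needs a period effect, and none is documented. Both periods share the sodium and caffeine restrictions, the minimum fluid replacement, the pre-dose void and the CRU stay. At π = 5% and 9/9 the interval widens by only 1.2% at CV 20% (0.3% at CV 30%, 5.9% at CV 10%). At π = 10% and CV 20%, the bias is about 4% of the half-width at 11/10, 8% at 10/8 and 15% at 11/7. PD has no decision rule. All of this stands, and it limits the size of the point. The shared conditions make a large period effect less likely but do not exclude one, and the term costs almost nothing.

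A reader might infer three stronger things that the documents do not support:
- That the CI is too wide regardless. Below the break-even, omitting period costs nothing.
- That leaving out period produces false-positive PD findings. It does not at splits up to 11/7. The rate exceeds nominal only with much greater imbalance (6-11% at 14/7), and a 1:1 ratio alone neither predicts nor excludes such a split.
- That the 20-37% rates are a consequence of omitting period, or that the SAP has chosen independent residuals. SAP 9.2 says within-subject correlations are accounted for but names no structure beyond random subject. The structure is unstated, so this is a request to specify it.

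**Conclusion.** The omission is certain; its consequence is conditional and small. If a PD period effect exists, unequal sequences bias the SC−IV difference by 0.5-2.2% of the mean for a 10% effect at splits from 11/10 to 11/7. Equal sequences give no bias but a wider interval once the effect passes about 0.1 SD of the paired difference. The period effects and CVs are assumptions, because the documents supply none.

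The bias formula is exact only for subjects with both periods. That fits the Bioavailability Population in which SAP 9.2 summarises PD, but SAP 8 also says "The subject demographics, baseline characteristics and the other endpoints will be based on the Full Analysis Set (FAS) population". If incomplete pairs enter the model, the formula changes.

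The unstated covariance is a separate gap. It would matter more than period if residuals were taken as independent. Overall the stakes are minor: PD is a secondary objective to describe, and the primary AUC analysis already contains period.

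**What to change.** The cleaner option is to fit the SAP 9.1 crossover model (sequence, subject within sequence, period, treatment) separately to the 0-6, 0-8 and 0-12 h totals, with n−2 error df.

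The alternative is to keep the mixed model and add period and period-by-time, an unstructured covariance across the three windows within a period, and a stated small-sample df method. A period main effect alone is not enough, because the effect may differ between cumulative windows. With effects of 10/20/30% by window at 11/7, it removes the average of 20% and leaves (−10, 0, +10) × 4/18 = −2.2/0/+2.2% of the mean. Nor should period be added with independent residuals: the false-positive rate then stays at 22/33/38% for window correlations of 0.5/0.8/0.95.

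In the same edit, state which population the PD model uses.

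The cost is a few lines of SAP text, no new data and one error df per window. If there is no period effect, the half-width at CV 20% grows by under 0.1 point of the mean at 9/9 and by about 0.4 at 11/7 (13.9 to 14.3). Against the independent-residual reading, the across-window half-width rises from about 6% to 13-14% of the mean, which is the correct width under these assumptions.
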